#### 3. STUDY OBJECTIVES AND ENDPOINTS

# 3.1. Study Objectives

#### 3.1.1. Primary Objective

 To confirm ORR in iCCA patients with FGFR2 gene fusions or other FGFR2 rearrangements based on independent central radiology review.

#### 3.1.2. Secondary Objectives

- To evaluate DOR
- To evaluate the safety and tolerability of TAS-120
- To evaluate DCR, PFS, and OS
- To evaluate Patient-Reported Outcomes (PROs)

CCI

### 3.2. Study Endpoints

#### 3.2.1. Primary Endpoint

Objective response rate (ORR) according to RECIST 1.1 guidelines. Objective response rate is defined as the proportion of patients who had best overall response (BOR) of CR or PR based on independent central radiology review.

#### 3.2.2. Secondary Endpoints

Duration of response (DOR)

Duration of response is defined as the time from the first documented response (CR or PR) to the first documented objective progressive disease (PD) or death due to any cause.

Disease control rate (DCR)

Disease control rate is defined as the proportion of patients with objective evidence of CR, PR, or SD, except that there is no requirement for a confirmation of an SD response.

Progression-free survival (PFS)

PFS is defined as the time from the first dosing date to the date of the first documented progression or death due to any cause, whichever occurs first.

Overall survival (OS)

OS is defined as the time between the first dosing date and the date of death.

ORR, DOR, DCR and PFS endpoints will be calculated based on IRC and based on investigator assessment

#### • Safety and Tolerability of TAS-120

Safety will be analyzed through the incidence of death, adverse event, concomitant medications, physical examination, vital sign measurements, clinical laboratory results, ECG results, ECG performance status, and other safety observations at the time points indicated in the Study Schedule of Assessments (Table 1) will be monitored and recorded. The data will be summarized.

• Patient-Reported Outcomes (PROs)

#### EQ-5D

The EQ-5D descriptive system comprises the following 5 dimensions: mobility, self-care, usual activities, pain/discomfort and anxiety/depression. Each dimension has 3 levels: no problems, some problems, severe problems. Once the data have been collected and a database created, a scoring function can be used to assign a value (i.e., EQ-5D index score) to self-reported health states from a set of population-based preference weights.

The EQ VAS records the patient's self-rated health state on a 100-point vertical, visual analogue scale (0 = worst imaginable health state; 100 = best imaginable health state).

### **EORTC QLQ-C30**

Health-related quality of life (HRQoL) will be assessed using the European Organization for Research and Treatment of Cancer (EORTC) QLQ-C30 questionnaire Version 3. It is a 30-item instrument that has gained wide acceptance in oncology clinical studies. The EORTC QLQ-C30 is composed of multi-item and single scales. These include five functional scales (physical, role, emotional, social, and cognitive), three symptom (fatigue, nausea and vomiting, and pain) and a global health status/QOL scale and six single items (dyspnea, insomnia, appetite loss, constipation, diarrhea and financial difficulties). All scales and single items meet the standards for reliability. The reliability and validity of the questionnaire is highly consistent across different language-cultural groups. Except for the overall health status and global quality of life items, responses for all items are 4-point categorical scales ranging from 1 (Not at all) to 4 (Very much). The overall health status/quality of life responses are 7-point Likert scales.

# 4. STUDY DESCRIPTION

# 4.1. Summary of Study Design

[figure not shown]
This is an open-label, nonrandomized, Phase 2 study of TAS-120 (Futibatinib), evaluating the efficacy, safety, tolerability, PK and antitumor activity of TAS-120 in patients with Intra-hepatic cholangiocarcinoma (iCCA) with *FGFR2* gene fusions or other *FGFR2* rearrangements who have failed all standard therapies or for whom standard therapy does not exist.

The overall study design is described in Figure 1. Study schedule for this phase 2 study is presented in Table 1.

Figure 1: Study Schema

#### Approximately 100 treated patients

- Prescreening by local or Sponsor-designated central laboratory for FGFR2 gene fusion or other FGFR2 rearrangements in patients with histologically or cytologically confirmed, locally advanced, metastatic, unresectable iCCA.
- At least one prior systemic gemcitabine and platinum-based chemotherapy.
   Patients with prior adjuvant gemcitabine-platinum chemotherapy are eligible if the patient had recurrence within 6 months of the last dose of the regimen. Prior FGFR directed therapy is not permitted.
- Documentation of radiologic disease progression following the most recent prior therapy.
- Measurable disease as defined by RECIST guidelines (version 1.1, 2009).

ORR = Objective response rate; PFS = Progression-free survival; DCR = Disease control rate; DOR = Duration of response; OS = Overall survival; PROs = Patient-Reported Outcomes; PK = Pharmacokinetics.

In this study, patients will be followed for survival for up to 18 months after the last patient enrolled. The detailed study schedule is shown in Table 1.

# **Table 1:** Study Schedule for Phase 2

NOTE: Evaluations on D1 of a cycle should be performed within 24 hours prior to dosing, unless otherwise noted. Procedures already performed during the screening period within 72 hours prior to dosing do not need to be repeated on C1D1.

The EOT visit must be performed 0-7 days after the decision is made to discontinue study treatment (for patients who discontinue at a planned study visit, that visit may be considered the EOT visit if all assessments required at EOT are performed).

		Screening Period	Treatment Period (1 cycle = 21 days)					Safety Follow-up		Follow-	Notes
	Pre-	(Within 28 Days	Cycle 1				Cycles ≥2	of Tx	ays) days Last	7	
	Screening	Prior to First Dose)	Day 1	4 (±1d)	8 (±3d)	15 (±3d)	Day 1 (±3d)	End o (+0-7 d	30 (±3) After	Survival up Period	
Written informed consent	(X)	X									Pre-screening ICF if required for determination of eligibility.
Tumor tissue testing of FGFR2 gene fusions / rearrangements	provided if a		ses where								ntral laboratory, tumor tissue should be ust be submitted to central laboratory for
Review eligibility criteria		X	X								
Demographics/medical history		X									
Review of pre-existing signs and symptoms		X	X								
Physical examination		X	X				X	X	X		Within 24 hours prior to dosing on D1 of each cycle.
Vital signs		X	X				X	X	X		Heart rate, blood pressure, body temperature, and respiration rate.
Height and Weight		X	X				X	X	X		Height at screening only.
Ophthalmological examination		X					(X)	X	X		At screening and 4-6 weeks after first dose; additional on-study evaluation as needed due to local requirements, physician judgment, and/or symptoms or signs of mineral deposits.
Neurological examination		X	(X)				(X)	X	X		As clinically indicated after screening, using same methods used at screening.
ECOG performance status		X	X				X	X	X		Within 24 hours prior to dosing on D1 of each cycle.

Taiho Oncology, Inc. Statistical Analysis Plan (Phase 2) – Protocol TPU-TAS120-101

# 15 October 2020

		Screening Period	Treatment Period (1 cycle = 21 days)				Safety Follow-up		Follow-	Notes			
	Duo	Dna	Pre-	Dna	(Within 28 Days	Cycle 1			Cycles ≥2	End of Tx (+0-7 days)	days Last	-	
	Screening	Prior to First	Day				Day	1 of -7 da	(±3) er	Survival up Period			
		Dose)	1	4 (±1d)	8 (±3d)	15 (±3d)	1 (±3d)	End (+0-	30 (±3 After	on Jan			
12-Lead Electrocardiogram		x	X				X	X	X		At screening and 2 hours (±15 minutes)  after dosing on D1 of each cycle.		
Hematology and coagulation		x	x		x	X	x	X	X		Within 24 hours prior to treatment on D1 of each cycle, any time on C1D8 and C1D15, and as clinically indicated.		
Chemistry (Serum or plasma)		x	x	(X)	x	х	x	X	x		Within 24 hours prior to treatment on D1 of each cycle, any time on C1D8 and C1D15, and as clinically indicated. Additional collection for phosphorus only at C1D4.		
Urinalysis (Urine dipstick)		X	X				X	X	X				
Pregnancy test		x	x				x	X	x		Serum pregnancy test required for WOCBP at screening and end of treatment; serum or urine pregnancy test required at all other timepoints.		
Blood PK Sampling (Required)							x				Blood samples (1 mL) collected C2D1 pre-dose and at 1h and 3h (±30 min) post-dose. Additional samples collected pre-dose on C3D1 and C4D1.		
ctDNA blood samples		x						(X)			Minimum of 20 mL whole blood at screening (mandatory) and EOT (optional).		
CCI													
Prior & concomitant medications, AE assessments	х	x					→	x	x		Collect from the time main informed consent is signed through 30 days after administration of the last dose of TAS-120 or until the start of new anticancer therapy, whichever is earlier. AEs directly associated with a pre-screening procedure should be reported as described in Protocol Section 12.1		

		Screening Period	Treatment Period (1 cycle = 21 da	ıys)	Safety Follow-up	Follow-	Notes
	Pre-	(Within 28 Days	Cycle 1	Cycles ≥2	of Tx days) () days Last		
	Screening	Prior to First Dose)	Day  1	Day 1 (±3d)	End of Tx (+0-7 days) 30 (±3) days After Last	Survival up Period	
PRO (EQ-5D and EORTC QLQ-C30)		X	1 (±1d) (±3d) (±3d)	X	X	S. 1	Evaluated at screening and as close as possible to the tumor assessment schedule: at the end of every 2 cycles (up to +2 weeks) through Cycle 4 and every 3 cycles (±7 days) thereafter until disease progression or initiation of new anticancer therapy (whichever is first).
Tumor assessments / scans		X		X	X	(X)	Same tumor assessments/scans obtained at screening at the end of every 2 cycles (up to +2 weeks) up to Cycle 4. Thereafter tumor assessments may be performed every 3 cycles (± 7 days), or as clinically indicated, until radiologic PD or initiation of new anticancer therapy (whichever occurs first).  At EOT, tumor assessment must be performed if the prior scan was performed ≥9 weeks prior to discontinuation of treatment if the patient discontinued for reasons other than radiologic disease progression. See also Protocol Section 10.17.  After EOT, patients who discontinued for reasons other than radiologic disease progression should continue to receive tumor assessments every 3 cycles (± 7 days), or as clinically indicated, until radiologic disease progression or initiation of new anticancer therapy (whichever occurs first).

Taiho Oncology, Inc. Statistical Analysis Plan (Phase 2) – Protocol TPU-TAS120-101

# 15 October 2020

[figure not shown]
		Treatment Period (1 cycle = 21 days)					Safety Follow-up		Follow-	Notes	
	Pre-	Period (Within 28 Days	Cycle 1	I			Cycles ≥2	of Tx days)	days Last	o J	
	Screening	Prior to First Dose)	Day 1	4 (±1d)	8 (±3d)	15 (±3d)	Day 1 (±3d)	End o (+0-7 d	30 (±3) After	30 (±3) ds After L	
Survival status										X	After discontinuation of treatment, survival follow-up should occur every 3 months (±2 weeks) for up to 18 months after last patient enrolled in the Phase 2 portion of the study.
TAS-120 Dosing							>				Patients are required to fast for ≥2 hours before and 1 hour after each administration of TAS-120; patients are permitted to drink water. TAS-120 should be administered in the morning or evening, at the same time (if possible) each day. See protocol Section 9.1.1.

# 4.2. Treatment Assignment and Blinding/Unblinding

After the patient's initial eligibility is established and informed consent has been obtained, the 20 mg QD of TAS-120 (Futibatinib) will be administered orally in iCCA patients. The treatment of TAS-120 will be continued with 21-day treatment cycle until at least one of the criteria for study discontinuation criteria is met.

This is an open-label study. Blinding/unbinding is not applied.

# 4.3. Determination of Sample Size

# 5. STUDY PERIODS, TREATMENT REGIMENS, AND POPULATIONS FOR ANALYSIS

# 5.1. Study Periods

The study periods are defined in Table 3 below.

**Table 3** Definition of Study Periods for Analysis

Period	Definition
Baseline / Screening	From the day of ICF signature (up to 28 days before first dose) to the day and time of the first dose of study drug.
On-treatment	From the date of first dose of study therapy through 30 days after the last dose of study therapy. Unless otherwise specified, the on-treatment period will be the basis for the summaries of safety.

Abbreviations: ICF=informed consent form.

### 5.2. Treatment Regimens

TAS-120 will be administered continuously once daily on a 21-day treatment cycle until at least 1 of the criteria for study discontinuation is met. TAS-120 will be administered as outlined in Study Drug Administration (Protocol amendment 9, Section 9.1.1) and Dose Reduction/Modification Procedures (Protocol amendment 9, Section 9.1.3). There are no breaks in dosing between cycles.

# **5.3.** Populations for Analysis

- **Safety Population:** All patients who received at least 1 dose of TAS-120. This population will be the primary population for safety evaluation
- Efficacy Population: All Intra-hepatic cholangiocarcinoma (iCCA) patients who received at least 1 dose of TAS-120 with FGFR2 gene fusions or other FGFR2 rearrangements
- PRO Population: All patients who received TAS-120 treatment and had EQ-5D or EORTC QLQ-C30 assessment at baseline and at least one subsequent post-baseline assessment
- Per-protocol Patients (Per-Protocol Population): All treated subjects who have no relevant protocol deviations. For patients who have a relevant deviation during the study, data collected before the point of deviation can be included in the analysis preformed for this population.

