12.2.2.6. Patient-Reported Outcomes

The analyses of EQ-5D and EORTC QLQ-C30 will be performed in all treated patients who have an assessment at baseline and at least one subsequent assessment.

EQ-5D

Patient's overall health state on a visual analog scale (EQ-VAS) at each assessment time point will be summarized using descriptive statistics. Proportion of patient's reporting problems for the 5 EQ-5D dimensions at each assessment time point will be summarized by level of problem. Percentages will be based on number patients assessed at each assessment time point.

A by-patient listing of EQ-5D with the problem levels for each of the 5 dimensions (mobility, self-care, usual activities, pain/discomfort and anxiety/depression), health state (5 dimensions digits combined in a 5-digit number) and EQ-VAS will be provided.

EORTC QLQ-C30

All scales and single items are scored on a categorical scale and linearly transformed to 0-to-100 scales with higher scores for a functional scale representing higher levels of functioning, higher scores for the global health status/quality of life representing higher levels of global health status/quality of life, and higher scores for a symptom scale representing higher level of symptoms.

Baseline and change from baseline in EORTC QLQ-C30 global health status/quality of life (QoL) composite scale data and the remaining EORTC QLQ-C30 scale data will be summarized by time point using descriptive statistics for each cohort. In addition, the percentage of patients demonstrating a clinically meaningful deterioration (defined as a 10-point change from baseline) will be presented for each scale at each assessment time point. Percentages will be based on number patients assessed at each assessment time point.

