# 6.6. Patient Reported Outcomes (PRO)

Unless otherwise specified, the primary timepoint for the analysis of PRO endpoints is the last analysis visit before data is missing for more than 50% of the PRO population. This 'censoring' is done since when there is more than 50% missing data, reported PRO scores will be very sensitive to missing data assumptions. The primary assessment timepoint for the PRO analysis will be determined based on a data review prior to the database lock.

All EQ-5D and EORTC-QLQ-C30 questionnaires completed at baseline and on-study will be assigned to a time-point according to the windowing criteria in Table 12 and included in the analysis. In case a patient has two on-study assessments within the same window, the assessment closest to the time-point will be used. And, in the case of two assessments at a similar distance to the time-point, the latest one will be chosen. In the event where the patient has no assessment at all in a specific window, the observation will be treated as missing for that time-point.

Table 12. Time Windows for EQ-5D and EORTC-QLQ-C30 Assessment

Nominal Time-Point	Time Window
Screening	-28 to -1 days
Cycle 2, Cycle 4	Day $1 \pm 3$ days
>Cycle 4	Every 3 cycles on day 1 of the cycle $\pm$ 7 days
End of Treatment	Within 3 days of the decision to discontinuation

The Patient-Reported Outcomes (PRO) will be evaluated as close as possible to the tumor assessment schedules.

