#### **Symptom scales/items:**

Fatigue: ((Q10+Q12+Q18)/3-1)/3 \* 100

Nausea and vomiting: ((Q14+Q15)/2-1)/3 \* 100

• Pain: ((Q9+Q19)/2-1)/3 \* 100

Dyspnea: ((Q8-1)/3 \* 100
 Insomnia: (Q11-1)/3 \* 100

Appetite loss: (Q13-1)/3 \* 100

Constipation: (Q16-1)/3 \* 100

Diarrhea: (Q17-1)/3 \* 100

Financial difficulties: (Q28-1)/3 \* 100

Missing values will be imputed for missing items by "assuming that the missing items have values equal to the average of those items which are present" for any scale in which at least half the items are completed. A scale in which less than half of the items are completed will be treated as missing. A questionnaire will be considered as received if at least one of the 15 scales is non-missing (after imputation). All scales and single items are scored on a categorical scale and linearly transformed to 0-to-100 scales with higher scores for a functional scale representing higher levels of functioning, higher scores for the global health status/quality of life representing higher levels of global health status/quality of life, and higher scores for a symptom scale representing higher level of symptoms.

PRO endpoints relating to the EORTC QLQ-C30 are as follows:

- Change from screening in each EORTC QLQ-C30 scale
- Time to first deterioration in the EORTC QLQ-C30 global health status and physical functioning scores
- Proportion of patients with deterioration based on the EORTC QLQ-C30 global health status and physical functioning scores

Baseline and change from baseline in EORTC QLQ-C30 global health status/quality of life (QoL) composite scale data and the remaining EORTC QLQ-C30 scale data will be summarized by time point using descriptive statistics for each cohort. In addition, the percentage of patients demonstrating a clinically meaningful deterioration (defined as a 10-point change from baseline) will be presented for each scale at each assessment time point. Percentages will be based on number patients assessed at each assessment time point.

The changes values from baseline to post-baseline and shift evaluation from baseline to post-baseline will be summarized.

Time to deterioration (TTD) of PRO scores is defined as the period between PRO at screening and the first deterioration (including death). Patient who did not have post-baseline deterioration will be censored on the last date of assessment.

CC

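### Time to deterioration counts death as an event, but the PRO Population leaves out patients who die before returning any post-baseline form

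*SAP*

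**What the plan says.** Phase 2 SAP section 5.3 defines the PRO Population as treated patients who "had EQ-5D or EORTC QLQ-C30 assessment at baseline and at least one subsequent post-baseline assessment". Protocol section 12.2.2.6 says the EQ-5D and QLQ-C30 analyses will be "performed in all treated patients who have an assessment at baseline and at least one subsequent assessment". SAP section 6.6 takes the same population as its base: the primary PRO time point is "the last analysis visit before data is missing for more than 50% of the PRO population".

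SAP section 6.6.2 lists among its endpoints "Time to first deterioration in the EORTC QLQ-C30 global health status and physical functioning scores". Its definition reads "Time to deterioration (TTD) of PRO scores is defined as the period between PRO at screening and the first deterioration (including death", so death is an event. The censoring rule is "Patient who did not have post-baseline deterioration will be censored on the last date of assessment". The TTD paragraph names no analysis set of its own.

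On collection, protocol section 9.18 asks for forms at screening, at the end of every second cycle up to Cycle 4 (with up to two weeks' leeway), every third cycle after that, and at end of treatment. Section 9.19 requires the end-of-treatment visit of living patients only.

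**The concern.** Entry to the PRO Population depends on something that happens after treatment starts: the patient must live long enough, and be well enough, to return a second form. That is a reasonable condition for a change-from-baseline summary, which cannot be computed without a second score. It is not reasonable for an endpoint in which death is itself an event, because the earliest deaths are the patients the condition removes.

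No death can appear on the TTD curve before that patient's own first post-baseline form. Any such deaths in the trial are lost, and the error always runs in the favourable direction. Phase 2 is single-arm, so no comparator carries the same bias.

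**Working it through.** The documents print no figure for this point, so there is nothing to reproduce. The check sets the definitions together and then sizes the effect under stated assumptions.

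**Inputs from the documents**
- Cycle length 21 days (protocol 8.1.2). The first scheduled on-study form is at the end of Cycle 2: 2 × 21 = day 42, or up to 42 + 14 = day 56. SAP Table 12 labels its first on-study window as Day 1 of Cycle 2, which does not match. I use the collection schedule in protocol 9.18 and SAP Table 1; the argument does not depend on which is right.
- An end-of-treatment form may come earlier, but only from a living patient (protocol 9.18 and 9.19).
- About 100 treated patients (SAP 4.1).

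**Assumed, because the documents do not give it:** the number *d* of patients who die before any post-baseline form, taken as 0, 2, 5 or 10 per 100.

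**Step 1: who is excluded.** A patient who dies on day 30 with no form has a TTD event under SAP 6.6.2 but fails the condition in SAP 5.3 and protocol 12.2.2.6. No text restores that patient.

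**Step 2: effect on the curve.** Let *N* be the patients at risk after time zero and S_PRO(t) the estimate in the *N* − *d* who remain. With no censoring before the early deaths, at later times

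S_all(t) = S_PRO(t) × (N − d)/N.

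With *N* = 100 and an assumed reported value of 60% at 6 months:
- d = 0: 0.60 × 100/100 = 0.60
- d = 2: 0.60 × 98/100 = 0.588, about 59%
- d = 5: 0.60 × 95/100 = 0.57
- d = 10: 0.60 × 90/100 = 0.54

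**Step 3: illustrative Kaplan-Meier run.** Deaths are spread over days 10 to 40. The remaining patients have exponential event times starting at day 42, with a median of 150 days after that. There is no administrative censoring, and time zero is treated as first dose.

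| Early deaths per 100 | Deterioration-free at day 42, all vs PRO Population | At day 183 | Median TTD (days) |
|---|---|---|---|
| 0 | 100% vs 100% | 52.0% vs 52.0% | 190 vs 190 |
| 2 | 98.0% vs 100% | 51.0% vs 52.0% | 185 vs 190 |
| 5 | 95.0% vs 100% | 50.0% vs 52.6% | 179 vs 192 |
| 10 | 90.0% vs 100% | 47.0% vs 52.2% | 167 vs 190 |

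The median is longer by roughly 5, 13 and 23 days. The small movement in the PRO Population column (190, 192, 190) comes from the discrete event times.

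**Step 4: living patients with no form.** Their only assessment is the screening form, so the SAP rule censors them at time zero. They leave the risk set before any event and add nothing. Adding 5 such patients with no early deaths gave the same curve with or without them. If 8 of 100 have no form and 3 of those died, the corrected value is 0.60 × 92/95 = 0.581, about 58%.

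**The case against.** **The link to TTD is inferred.** The TTD paragraph names no population, and protocol 12.2.2.6 does not mention TTD. This is correct. But the protocol restriction covers the analyses of both instruments without exception, and SAP 6.6 is built on the PRO Population. If another set was intended for TTD, the SAP should name it.

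**The end-of-treatment form catches early leavers.** In part. A patient who declines and stops before the end of Cycle 2 is due a visit within 7 days and can enter the population that way. A patient who dies on treatment cannot. Protocol 9.20 also lets the 30-day safety visit replace the end-of-treatment visit when the two fall within 14 days of each other, and 9.18 does not list a form at the 30-day visit.

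**Early deaths may be few, and they are visible.** Entry requires ECOG 0 or 1 and adequate organ function. SAP 6.3.1 reports the size of each population, SAP 6.5.2.1 summarises and lists deaths, and OS is analysed separately. All of this stands. It lets a reader see that patients are missing, but it does not correct the TTD curve.

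**Two stronger readings are tempting and not supported.** A reader might treat every patient without a post-baseline form as a lost event; with 5, 8 or 15 per 100 that turns 60% into 57%, 55% or 51%. Those figures hold only if every such patient died, because living ones are censored at time zero. A reader might also infer that the proportion with deterioration is biased downward. SAP 6.6.2 bases the by-visit percentages on a 10-point change among patients assessed at that visit, so a patient with no form is outside the denominator under either population. The separately listed proportion with deterioration would be affected only if it were cumulative and counted death, which the SAP does not say.

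**Conclusion.** The point holds, limited to deaths before any post-baseline form and to TTD. The analysis set and the event definition conflict, and the resulting bias can only lengthen TTD. Its size is proportional to the number of such deaths, which the documents do not give: about 1, 3 or 6 percentage points off a reported 60% for 2, 5 or 10 deaths per 100, and nothing if there are none. A living patient with no form matters only if a death is recorded later.

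This assumes that TTD uses the PRO Population, which is the only reading the text offers, and that there is no censoring before the early deaths. PROs are among the other secondary objectives, the visible text sets no TTD threshold, and the primary ORR analysis is unaffected. The correction is worth making because it is cheap and the error runs one way.

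**What to change.** In SAP sections 5.3 and 6.6.2, define a separate set for TTD: all treated patients with a baseline QLQ-C30 form. Within it:
- count death before the first on-study form as an event on the date of death;
- censor survivors with no post-baseline form at the date of the screening form, which is what the existing last-assessment rule implies;
- report the number of patients in each of these categories.

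Keep the PRO Population for the change-from-baseline summaries. SAP Table 6 already works in a similar way for PFS: death without progression is an event, and a patient who stops treatment with no post-baseline scan is censored at the start (there, first dose).

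No new data are needed, since survival status is collected under protocol 9.21. The costs are a slightly less favourable TTD and a departure from protocol 12.2.2.6, which should be recorded as a change from the protocol-specified analysis.
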